5.2.1. Identification of COVID-19 cases for adjudication

All COVID-19 episodes and/or SARS-cov-2 infections since the start of the study will be identified using a programmed algorithm described in the section 5.2.2. All fatalities that occur within the study for which COVID-19 could be a contributory or the underlying cause of death will be sent for adjudication, including fatalities not identified by the programmed algorithm. In

addition, cases may be flagged for adjudication through the use of other sources such as the Global Medical Safety database.

All cases identified by the algorithm as severe/critical (tier I)^a or mild (tier V)^a will be sent for adjudication for review on a case by cases basis.

Similarly, moderate cases identified by the algorithm will be sent for adjudication when they have at least one flag=Y for (tier II):

- SpO₂ ≤93% from any source
- Heart rate ≥125 beats/minute
- Respiratory Rate ≥30 breaths/minute
- Medical Attended/MA-COV

In addition, a moderate case identified by the algorithm that resulted in hospitalization will be sent for adjudication.

For all other cases identified by the algorithm as moderate (tier III if 3 or more signs/symptoms, tier IV if <3 signs/symptoms)^b, adjudication may be performed for only a proportion of such cases, i.e. a sample approach. That is, the CSAC will be presented with the programmed algorithm outcomes and be asked to review a sample of such cases. Based on the results of these “sample adjudications”, the CSAC will make a recommendation whether the programmed algorithm can serve as the default method of adjudication for the remainder of such cases.

Participants identified by the algorithm as asymptomatic/ undetected infections based on a PCR positive result during the course of their participation in the study and/or based on having seroconverted during their study time will be sent for adjudication only when the algorithm captures the presence of COVID-19 symptoms at any point up to 7 days prior to the onset of an algorithmic asymptomatic SARS-CoV-2 infection or prior to seroconversion.

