5.2.2. COVID-19 case classification relevant definitions

Definitions relevant to COVID-19 case classification are listed below.

- **Episode** (of COVID-19): An episode of COVID-19 is defined as the period of the onset of (COVID-19) symptoms up until resolution of the episode. The severity of a COVID-19 will be determined based on the maximum severity observed across the episode.
- **Onset of (COVID-19) symptoms:** This is the date when any sign(s) or symptom(s) suggesting possible COVID-19. It will be called Day 1 of an episode. It is the earliest date the first symptom of an episode entered on the eCOA or on the CRF if entered by the site (“*If a participant records in the eCOA or informs the site that he/she experienced any signs or symptoms suggesting possible COVID-19, this will be considered COVID-19 Day 1 (day of onset of signs and symptoms).*” CTP) or the AE onset date if linked to COVID-19 (The following preferred terms are included in this analysis: "COVID-19", "ASYMPTOMATIC COVID-19", "SUSPECTED COVID-19", "COVID-19 PNEUMONIA" and "SARS-COV-2 TEST POSITIVE"). [Day 1 will be derived based on the first symptoms that are entered in the eCOA before the first swab is taken. In case there are multiple days with symptoms entered in the eCOA before the first swab, Day 1 is the earliest Day of all consecutive Days with signs or symptoms that are at least mild. Days without symptoms within 7 days before the first swab will be ignored in the evaluation of consecutive days.] A sensitivity analysis will be done to evaluate the change in onset date based on the 7 day window compared to the algorithm implemented at the primary analysis, where a day without symptoms interrupted the consecutive Days.
- **Resolution of an episode:** Resolution of the COVID-19 episode is defined as having 2 consecutive SARS-CoV-2 negative nasal swabs and 2 consecutive days with no COVID-

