5.2.5.2. Classification

As for symptomatic COVID-19 case classification, a similar approach will be taken to identify asymptomatic infections or undetected cases via an algorithmic approach. Cases will then be reviewed and classified as being an "Asymptomatic SARS-CoV-2 infection" by the Clinical Severity Adjudication Committee.

Relevant definitions for programmed algorithm:

Identification of potential asymptomatic SARS-CoV-2 infections via PCR: in the event of a positive PCR, the cases will be reviewed for the presence of signs and/or symptoms of COVID-19 since baseline employing the definitions of onset and resolution of section 5.2.2. In the absence of signs and/or symptoms, the case will be classified per algorithm as asymptomatic.

Identification of potential asymptomatic or undetected SARS-CoV-2 infections through seroconversion:

- **SARS-CoV-2 seroconversion with onset Day >28** is based on the available data from Day 71, Month 6 and/or unblinding visit. If positive at any timepoint while the subject was seronegative at baseline (and at Day 29 for the PP analysis after day 28), a subject is considered seroconverted. If Day 29 is missing or not available, then the subject is considered negative on that Day.
- **SARS-CoV-2 seroconversion from Day 1 to Day 29**, is based on the available data on day 29. If positive at day 29 while the subject was seronegative at baseline or missing, a subject is considered seroconverted between day 1 and day 29.

- A **seroconverted participant** is a subject with serological conversion without an earlier molecularly confirmed (SARS-CoV-2 positive RT-PCR or molecular test result from any available respiratory tract sample)

Upon algorithmic identification, cases will be evaluated as being an "Asymptomatic SARS-CoV-2 infection" by the Clinical Severity Adjudication Committee as follows:

- Asymptomatic SARS-CoV-2 infections or seroconverted participants as assigned via the programmed algorithm will be reviewed for the presence of possible COVID-19 signs and symptoms since baseline up to 7 days prior to the first positive PCR or up to the day of the first positive serology test.
- If no presence of signs/symptoms, the algorithm will be accepted and no further review by the CSAC and the case classified as Asymptomatic SARS-CoV-2 infections .
- If at least one sign or symptom present, those cases will be sent to the CSAC for review for a possible undetected symptomatic COVID-19.

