5.5.2. Key Confirmatory Secondary Endpoint(s) and Estimand(s)

5.5.2.1. Definition of Endpoint(s)

Endpoint Label	Endpoint definition
Any symptomatic infection (BOD)	
For all subjects with a symptomatic, molecularly confirmed COVID-19 episode, classification based on any severity will be included.
 
Weight-adjusted analysis for severe disease will be done as follows. Any case of mild or moderate COVID-19 will be given a score of 1, severe/critical COVID-19 cases will be given a score of 2.
 
Subjects without a symptomatic, molecularly confirmed COVID-19 episode are implicitly categorized as 0.

Asymptomatic infection	
Asymptomatic infection with an onset at least 28 days after vaccination is considered as a subject with either serologic conversion (day 71 or month 6) or with a SARS-CoV-2 positive RT-PCR or molecular test result from any available respiratory tract sample (eg, nasal swab sample, sputum sample, throat swab sample, saliva sample) or other sample but both without a previous suspected, symptomatic COVID-19 episode according to the adjudication committee (asymptomatic as defined in section 5.2.5). Additionally, both types of asymptomatic infections will be analyzed separately as well (based on PCR versus based on serology).

	
Supportive endpoints:
 
 1. Seroconverted participants will be defined as participants with a serologic conversion (day 71 or Month 6 and/or unblinding visit) and without a previous SARS-CoV-2 positive RT-PCR or molecular test result from any available respiratory tract sample (eg, nasal swab sample, sputum sample, throat swab sample, saliva sample) or other sample regardless of prior symptoms 2. Subset of asymptomatic infections based on PCR results from the Month 6 and/or unblinding visit 3. Asymptomatic infections between Day 1 and Day 29 will also be analyzed as a supportive endpoint. If positive at Day 29, while the subject was seronegative at baseline, a subject is considered seroconverted.
All infections (Any SARS-CoV-2 Infection)	First occurrence of SARS-CoV-2 infection (serologically, including serologically symptomatic confirmed, and/or molecularly confirmed ^a) with onset at least 28 days after double-blind vaccination with study vaccine.

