5.5.4.3. Any SARS-CoV-2 infections and asymptomatic infections

The proportion of subjects (out of subjects with available measurements) who serologically converted will be graphically visualized and tabulated at every available timepoint by randomized group, together with the number of subjects with an available measurement.

Additional tabulation will summarize the number of subjects with and without a SARS-CoV-2 infection as having

1. Not infected
2. Asymptomatic infections
 - Based on serological conversion
 - Based on positive RT-PCR
3. Symptomatic molecularly confirmed, with mild COVID-19
4. Symptomatic molecularly confirmed, with moderate COVID-19
5. Symptomatic molecularly confirmed, with severe COVID-19
6. Symptomatic serologically confirmed, with mild COVID-19
7. Symptomatic serologically confirmed, with moderate COVID-19
8. Symptomatic serologically confirmed, with severe COVID-19

A subject will be classified based on their worst occurrence and in one category only.

All subjects with multiple SARS-CoV-2 molecularly confirmed infections during the study will be tabulated by severity and double-blind vaccination group in the FAS-SN as well as SP set.

To assess the effect of Ad26.COV2.S on occurrence of any infection with SARS-CoV-2 as compared to placebo, VE will be estimated with an associated 95% confidence interval. If the timepoint of hypothesis testing is reached (when at least 15,000 subjects with a Day 71 available sample), adjusted two-sided (1- $2\alpha^*$) confidence interval (methodology described in Appendix 8). The alpha-level α^* is derived as detailed in section 2. To evaluate the hypothesis $H_0: VE \leq 0$, the

lower-limit of the adjusted confidence interval will be compared to 0, the hypothesis of protection against infection will be rejected.

To understand the vaccine efficacy of Ad26.COV2.S on occurrence of asymptomatic infections with SARS-CoV-2 alone, as compared to placebo, the VE will be estimated with a 95% confidence interval. If the timepoint of confirmatory testing is reached (when all participants have at least 6 months of follow-up), an associated adjusted two-sided (1- $2\alpha^*$) confidence interval (methodology described in Appendix 8). The alpha-level α^* is derived as detailed in section 2. To evaluate the hypothesis $H_0: VE \leq 0$, the lower-limit of the adjusted confidence interval will be compared to 0, the hypothesis of protection against infection will be rejected.

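### The symptom windows for asymptomatic infection disagree, and those that decide referral, review and the endpoint have no period after the positive swab

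*SAP*

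**What the plan says.** The SAP describes the search for symptoms in several places, with different time limits.

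- **Definition (5.2.5.1).** An asymptomatic or undetected infection is a positive PCR or non-S serology in someone who does not meet a mild, moderate or severe definition. No time limit is set.
- **Algorithm step (5.2.5.2).** PCR positives are "reviewed for the presence of signs and/or symptoms of COVID-19 since baseline employing the definitions of onset and resolution of section 5.2.2". No upper limit is stated. The borrowed onset definition (5.2.2) says, for eCOA data: "Day 1 will be derived based on the first symptoms that are entered in the eCOA before the first swab is taken".
- **Referral (5.2.1).** Algorithm-asymptomatic cases go to the CSAC only for symptoms "at any point up to 7 days prior to the onset of an algorithmic asymptomatic SARS-CoV-2 infection or prior to seroconversion".
- **Review (5.2.5.2).** Symptoms are sought "since baseline up to 7 days prior to the first positive PCR or up to the day of the first positive serology test". Otherwise: "If no presence of signs/symptoms, the algorithm will be accepted and no further review by the CSAC".
- **Confirmatory endpoint (5.5.2.1).** Seroconversion or a positive PCR counts, "but both without a previous suspected, symptomatic COVID-19 episode according to the adjudication committee".
- **Tabulation (5.5.4.3).** "A subject will be classified based on their worst occurrence and in one category only".

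PCR at the Month 6/unblinding visit is a named component of the objective (1.1) and a supportive subset of its own (5.5.2.1). That visit also ends the double-blind observation period (5.1.4, 5.1.5).

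**The concern.** The unblinding-visit swab is scheduled, not prompted by symptoms, so it can catch infections in their presymptomatic phase. The three rules that settle such a case contain nothing after the swab. A participant with no earlier symptoms is accepted as asymptomatic without CSAC review, even if illness follows within days.

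Read literally, the review window also ends 7 days before the positive PCR and so omits symptoms in the week before the swab. The wording in 5.2.1 could instead mean the 7 days leading up to onset. The text does not settle which is meant.

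Asymptomatic infection is a key confirmatory secondary endpoint, tested at the end of the double-blind phase (section 2). Presymptomatic cases bring the VE against symptomatic disease into an estimate meant for asymptomatic infection. They would also enter the Wilcoxon comparison of viral load in asymptomatic cases at the unblinding visit (5.6.1.2).

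**Working it through.** The SAP gives no figure for this misclassification, so there is none to reproduce. The check has two parts.

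**1. One participant under each rule.** Take a seronegative participant with no earlier symptoms who is PCR-positive at the unblinding visit and meets the mild definition a few days later.

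- 5.2.5.1: not asymptomatic, because no time limit applies.
- 5.2.5.2, algorithm step: unclear. No upper limit is stated, but the eCOA onset rule it borrows uses entries before the swab.
- 5.2.1, referral: not referred.
- 5.2.5.2, review: nothing in the window, so accepted as asymptomatic.
- 5.5.2.1, endpoint: counts, because no episode came before.
- 5.5.4.3, table: symptomatic, if the later illness is included.

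**2. Direction and size.** Inputs from 3.5.3 and Table 4:

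- placebo symptomatic cases: 20% mild, 60% moderate, 20% severe;
- VE 60% against mild and 70% against moderate/severe;
- VE against asymptomatic infection 30%, 40% or 50%.

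Overall symptomatic VE = 0.2 × 60% + 0.8 × 70% = 68%.

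Let f be the presymptomatic share of placebo PCR positives counted as asymptomatic. Then

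VE observed = 1 − [(1 − f)(1 − VE asym) + f(1 − VE sym)] = VE asym + f × (VE sym − VE asym).

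The gap is 68 − 30 = 38, 68 − 40 = 28 or 68 − 50 = 18 points. The SAP gives no f; 10-30% is an assumption.

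| True asymptomatic VE | f = 10% | f = 20% | f = 30% |
|---|---|---|---|
| 30% | 33.8% | 37.6% | 41.4% |
| 40% | 42.8% | 45.6% | 48.4% |
| 50% | 51.8% | 53.6% | 55.4% |

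The shift in PCR-based VE runs from 0.1 × 18 = 1.8 to 0.3 × 38 = 11.4 points.

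For the combined PCR-plus-serology endpoint, multiply by w, the share of placebo asymptomatic events that come from the unblinding swab. With w assumed at 10-50%, the shift runs from 0.1 × 0.1 × 18 = 0.2 to 0.5 × 0.3 × 38 = 5.7 points.

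The sign depends on the gap. With both VEs at 50% the shift is zero. With symptomatic VE 30% and asymptomatic VE 50%, it is 0.2 × (30 − 50) = −4 points at f = 20%.

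**The case against.** A reader might infer that every rule looks only before the positive PCR. The documents do not support that. The definition and the initial algorithm step set no upper limit. Elsewhere severity is the highest reached in the observation period (5.2), symptoms at any time in an episode count (5.2.3), cases are normally adjudicated at resolution or 30 days after onset (5.2.1), and new information leads to re-adjudication (5.9.8). Later illness could be picked up by the twice-weekly surveillance (section 1) and form its own episode. The adjudication charter is separate and not shown.

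This narrows the point to inconsistency but does not remove it. If the initial step searched symptoms without limit, the later review would have little left to find, so the two steps do not fit together. The other rules act on an episode or a referred case, and the referral rule does not create one here.

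Four further objections carry weight.

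- The endpoint covers asymptomatic or undetected infection, not infection that never becomes symptomatic. That is defensible as a target, but 5.2.5.1 defines it without a time limit, so the SAP must choose.
- A descriptive worst-occurrence table may differ from an endpoint without error. The difference should then be stated.
- PCR-based and serology-based infections are also analysed separately (5.5.2.1). That helps to reveal the effect but does not correct it.
- Counting all later symptoms automatically would bring its own bias. After the unblinding visit participants know their arm, and placebo recipients are offered the vaccine (5.1.4). One symptom is enough for a mild case (5.2.4.1), and fever, fatigue, headache and myalgia also stand on the vaccine reaction scale (Appendix 6). Reactions could move placebo infections out of the asymptomatic count and lower VE. This objection stands and shapes the fix.

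**Conclusion.** The symptom windows are inconsistent, and those governing referral, review and the confirmatory endpoint have no post-swab part. The same participant can be asymptomatic in the endpoint and symptomatic in the table.

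The consequence is a conditional upward bias: f × 18 to 38 points in the PCR-based asymptomatic VE under the SAP's planning values, or about 2 to 11 points at an assumed f of 10-30%. It is diluted in the combined endpoint, absent for seroconversions and minimal for any infection, where these cases count either way.

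A reader might infer that the confirmatory asymptomatic VE is certainly inflated by the full amount. The documents do not support that: the direction rests on symptomatic VE exceeding asymptomatic VE, f and w are not given, and the larger figures apply to PCR-detected cases only. The change should still be made, because it decides who counts in a key confirmatory endpoint.

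**What to change.** - Define one symptom window around the first positive PCR. It should cover the days before the swab and a stated period after it, and apply alike in 5.2.1, 5.2.5 and 5.5.2.1, consistent with 5.5.4.3.
- Send PCR positives with symptoms in that window to the blinded CSAC. Do not reclassify them automatically.
- State that a case judged presymptomatic leaves the asymptomatic endpoint, but does not become a double-blind symptomatic event if onset falls after unblinding.
- Report the asymptomatic VE and the unblinding-visit viral-load comparison with and without these cases as a sensitivity analysis, since the later symptoms are open-label and may be vaccine reactions in crossed-over placebo recipients.

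The cost is SAP wording, some programming and a few more adjudications. The symptom data are already collected, because surveillance continues after the unblinding visit. The drawback is reliance on some open-label symptom reports.

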5.2.6. Endpoint selection for analysis

Unless mentioned otherwise all clinical endpoints will be analyzed based on the assessment of the CSAC, supported by the algorithmic approach as explained above. Cases that are adjudicated as not a case by the CSAC are excluded from the analysis. Furthermore, for any symptomatic case to be included in this analysis there needs to be at least one SARS-CoV-2 positive RT-PCR or molecular test result from any available respiratory tract sample (eg, nasal swab sample, sputum sample, throat swab sample, saliva sample) that is confirmed by the central laboratory.

Supplementary analysis will include:

- An analysis based on the algorithmic classification as assigned above (limiting to centrally-confirmed cases)
- An analysis based on any documented positive PCR irrespective of the source (central confirmation, local site, Covance, external positive to the study) according to the accepted/reviewed severity and onset date by the CSAC

- An analysis will be done including suspected cases adjudicated by the CSAC.

A sensitivity analysis will be done based upon the algorithmic classification from the primary analysis.

5.3. Participant Dispositions

Participant information will be shown for the full analysis set.

The number of participants in the following disposition categories will be summarized throughout the study by intervention group and overall:

- participants screened
- participants screen failed (and main reason for screen failure)
- participants in the FAS
- participants in the PP
- participants in the FAS but not in the PP (and reasons for not being in the PP)
- participants vaccinated and not randomized
- participants randomized and not vaccinated
- participants vaccinated with incorrect treatment
- participants who discontinued study (and reasons for termination)
- participants unblinded
- participants crossed over
- participants having another COVID-19 vaccine

Also, the number of participants and percentage per phase will be tabulated.

Graphical displays will be created for the follow-up time in the double blind phase for all subjects, by country, age, co-morbidities as well as by age crossed with co-morbidities will be visualized.

5.4. Primary Endpoint(s) Analysis

5.4.1. Timepoint of primary analysis

The interim monitoring for the primary analysis can start as soon as the following conditions are met:

1. A minimum of 6 COVID-19 primary endpoint cases for the ≥ 60 years age group with onset at least 28 days after double-blind vaccination

2. At least 42 cases meeting the primary endpoint definition of moderate to severe/critical COVID-19 with onset at least 28 days after double-blind vaccination
3. A subset of at least 5 cases meeting the definition of severe/critical COVID-19 with onset at least 28 days after double-blind vaccination

No interim evaluation will be done, until those conditions are fulfilled. Monitoring for efficacy will not start before the above conditions 1-3 are met.

The efficacy analysis will be triggered by either:

- a) An interim evaluation if all prespecified efficacy boundaries have been met simultaneously at the same calendar timepoint OR if at least 154 cases meeting the primary endpoint definition of moderate to severe/critical COVID-19 are observed for events with onset at least 28 days after double-blind vaccination

AND

- b) The above 3 conditions are met.

OR, alternatively,

If the prespecified non-efficacy has been met (evaluating events with start 14 days after vaccination) or when the harm boundary has been crossed. The decision rules for harm and non-efficacy are detailed in Section [5.9](#)

If an efficacy signal is triggered before the required 8-week follow-up after vaccination of 50% of the enrolled participants is reached, an additional analysis will be performed when that follow-up timepoint is reached. If the time between the efficacy signal and the required 8-week median follow-up is too short to make a difference in terms of preparing two analyses, then a single analysis will take place at the time of the 8-week median follow-up. The analysis at the time of the 8-week median follow-up is considered the primary analysis.

If more than 154 primary endpoints are observed for events with onset at least 28 days after double-blind vaccination before the 3 conditions above are met, a single analysis will take place as soon as the conditions are met, using the full 2.5% one-sided significance level.

